## Study Endpoints

The goal of this clinical trial is to evaluate the clinical and functional outcomes associated with transitioning satisfied Bausch + Lomb Infuse Multifocal (kalifilcon A) wearers to DAILIES TOTAL1 (DT1) Multifocal (delefilcon A) lenses.

### Primary Endpoint:

- The proportion of participants with CLDEQ-8 <12 after 2-weeks of wearing DAILIES TOTAL1 Multifocal (w finalized prescription)

### Secondary Endpoints:

- VAS in comfort, overall vision and satisfaction
- CLDEQ-8 score after two weeks of DT1MF wearing
- Other Likert statement related to experience with study lenses
- SANDE and satisfaction ratings after two weeks
- Functional scores using WPAI-SHP after two weeks
- Distance, intermediate and near binocular VA after two weeks (with DT1MF)

### Exploratory Endpoint

---

- Digital device average usage time with CLs

## Study Assessments

	Visit 1 Baseline	Visit 2 (~1 week after V1)	Visit 3 (~2 weeks after V2*
Informed Consent	X		
Eligibility Confirmation	X		
CLDEQ-8	X		X
SANDE	X		X
WPAI-SHP	X		X
DT1 MF Lens Fitting & Dispense	X	X (PI to optimize the power if needed)	
VAS, satisfaction Survey and other Likert statements			X
Safety Assessment		X	X

\*After wearing the finalized prescription

## Inclusion & Exclusion Criteria

### Inclusion Criteria:

- Age  $\geq 40$  years at the time of enrollment.
- Current satisfied wearer of Bausch + Lomb Infuse One-Day Multifocal (kalifilcon A) contact lenses in both eyes, CLDEQ-8  $< 12$  at baseline.
- Minimum wearing time of at least 8 hours per day, at least 5 days per week, for a minimum of 30 days prior to Visit 1.
- Best-corrected distance visual acuity (BCDVA) of at least 20/25 (0.18 LogMAR) or better in each eye.
- Manifest refraction within the parameters of the study lenses (e.g., Sphere: +6.00D to -10.00D; Add: Low, Med, High).
- Willingness to adhere to the study protocol, including the use of DAILIES TOTAL1 (DT1) Multifocal lenses for 8 hours per day, at least 5 days per week, and completion of all questionnaires (e.g. CLDEQ-8, SANDE, WPAI-SHP, VAS and other Likert question items).
- Ability to provide written informed consent and follow investigator instructions

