### STUDY OBJECTIVE

*The purpose of this study is to determine the comfort and vision of DAILIES TOTAL1 Multifocal contact lenses in a population of satisfied INFUSE One-Day Multifocal contact lens wearers*

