### STUDY HYPOTHESIS

*A high proportion ( $\geq 70\%$ ) of satisfied INFUSE One-Day Multifocal wearers will report asymptomatic dry eye status (CLDEQ-8  $< 12$ ) after 2 weeks of wear with DAILIES TOTAL1 Multifocal (DT1MF).*

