### SUPPORTS CLINICAL MESSAGE

*DAILIES TOTAL1 Multifocal provides excellent comfort, vision and satisfaction in satisfied INFUSE One-Day Multifocal wearers. A majority of patients would like to continue wearing the lens. X out of 10 would recommend to a friend/family.*

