## Study Design & Methodology

### Study Design

Prospective, open-label, single-arm refit study. Participants serve as their own control for exploratory endpoints using paired baseline and follow-up measures. No washout period is required to preserve real-world ecological validity.

Study duration per participant: approximately 3 weeks

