### Methodology:

#### Procedures

##### Visit 1 — Baseline/ Dispense

- Informed consent
- Eligibility verification (including confirm satisfaction with current InfuseMF)

Subjects will be asked the following question: “**Are you satisfied with your current (Infuse MF) contact lenses?**” Subjects must answer ‘yes’ to continue in study.

- CLDEQ-8 baseline assessment
- SANDE (Symptom Assessment in Dry Eye)
- WPAI-SHP (Work Productivity and Activity Impairment Questionnaire)
- Power and ADD of habitual Infuse lenses
- Visual Acuity (VA) High-contrast LogMAR visual acuity measured at distance (20ft), intermediate (60cm), and near (40cm) with Infuse MF
- Daily average time of digital device usage while wearing habitual contact lenses (including tablet, phone, computer, TV and etc)
- Manifest Refraction
  - Refit into DAILIES TOTAL1 Multifocal
- Visual Acuity (VA) High-contrast LogMAR visual acuity measured at distance (20ft), intermediate (60cm), and near (40cm) with DT1 MF
- DT1mf Lens dispense

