#### **2. Potential Benefits of Participation**

- a. Subjects enrolled in this study may experience an improvement in the clinical signs and symptoms of their dry eye disease.

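### Entry and the primary endpoint share the same CLDEQ-8 cut-off of 12, so the endpoint measures retention from 100%; the 70% threshold and the named population do not reflect this

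*Protocol*

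**What the plan says.** **Entry.** The Protocol's Inclusion Criteria require a "Current satisfied wearer of Bausch + Lomb Infuse One-Day Multifocal (kalifilcon A) contact lenses in both eyes, CLDEQ-8" score below 12 at baseline. Study Considerations, item 1, requires the Visit 1 assessments to be made in the habitual Infuse lenses.

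**Satisfaction.** At Visit 1 it is established by a single yes/no question about the current lenses: "Subjects must answer ‘yes’ to continue in study". The CLDEQ-8 limit is a further condition.

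**Primary endpoint.** "The proportion of participants with CLDEQ-8 <12 after 2-weeks of wearing DAILIES TOTAL1 Multifocal (w finalized prescription"). The Executive Summary, Statistical Analysis and Sample Size Justification use the same instrument and cut-off.

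**Hypothesis.** "A high proportion ( $\geq 70\%$ ) of satisfied INFUSE One-Day Multifocal wearers" will report asymptomatic status after two weeks in the study lens.

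**Population named.** The Study Objective speaks of comfort and vision "in a population of satisfied INFUSE One-Day Multifocal contact lens wearers". The intended message is that "DAILIES TOTAL1 Multifocal provides excellent comfort, vision and satisfaction in satisfied INFUSE One-Day Multifocal wearers". Neither mentions the CLDEQ-8 limit.

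**Design and analysis.** "Prospective, open-label, single-arm refit study", 30 completers, a proportion with an exact Clopper–Pearson 95% interval, declared exploratory.

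**Benefit statement.** "Subjects enrolled in this study may experience an improvement in the clinical signs and symptoms of their dry eye disease".

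**The concern.** The endpoint variable, dichotomised at the same point, is also an entry criterion. All participants satisfy the endpoint before the study lens is fitted, so the proportion can only hold or fall. The endpoint shows how many asymptomatic wearers remain asymptomatic after a refit. It does not show how many attain comfort. The Protocol never calls it retention, never sets 70% against the 100% start, and gives no limit for worsening: Study Considerations, item 3, defines only a meaningful improvement, a decrease of 3 points or more.

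Two things are at stake. A reader shown 70% without the starting point may take it as favourable. And the conclusion is worded for satisfied wearers, although those who answer yes to the satisfaction question but score 12 or more never enter. The Background section says the results should help clinicians who are considering transitions, so the restriction affects how the result is used.

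**Working it through.** **Plan's own figure.** N = 30 cannot be reproduced. The Sample Size Justification rests on past research and the Central Limit Theorem and gives no error rates, expected proportion or null proportion. The only benchmark is the hypothesis's 70%, which is 0.70 × 30 = 21 of 30.

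**Step 1: baseline value of the endpoint.** Entry requires a score below 12 and success is a score below 12. Baseline success is therefore 30/30 = 100%.

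**Step 2: what just meeting the hypothesis means.** Exact 95% limits for x of n are the 2.5% quantile of Beta(x, n−x+1) and the 97.5% quantile of Beta(x+1, n−x).

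| Outcome | Proportion | Exact 95% CI |
|---|---|---|
| 21/30 still below 12 | 70.0% | 50.6% to 85.3% |
| 9/30 newly at 12 or more | 30.0% | 14.7% to 49.4% |
| 26/30 still below 12 | 86.7% | 69.3% to 96.2% |
| 27/30 still below 12 | 90.0% | 73.5% to 97.9% |

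A point estimate of 70% meets the hypothesis as worded. For the lower limit to exceed 70%, 27/30 would be needed.

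**Step 3: what to expect if the lens change had no effect.** The documents give no CLDEQ-8 mean, SD or retest reliability, so these are assumptions. Take two scores, bivariate normal with common mean m, SD s and correlation r, and compute P(second < 12 | first < 12). The lower figure in each range treats scores as whole points (cut at 11.5), the upper as continuous (cut at 12).

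| m, s, r (assumed) | Stay below 12 with no lens effect |
|---|---|
| 6, 4, 0.9 | 0.97 to 0.98 |
| 8, 5, 0.8 | 0.90 to 0.91 |
| 10, 6, 0.7 | 0.80 to 0.81 |

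The no-effect reference is thus about 80% to 98%. It is below 100% because people selected for a score below 12 will sometimes score higher on retest.

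**Step 4: chance of an observed 70% or more.** P(X ≥ 21) for X ~ Binomial(30, p):

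- p = 0.80: 0.939
- p = 0.90: 0.9995
- p = 0.70: 0.589
- p = 0.60: 0.176

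With no lens effect the threshold is met with probability about 0.94 or more (0.93 if the lowest reference is left unrounded at 0.795). Meeting it therefore says little about the lens.

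**Step 5: population gap (illustration).** Let a share u of satisfied wearers score 12 or more on Infuse, and let a share q of those score below 12 on the study lens. Neither is in the documents. With 70% in the enrolled group, the rate among satisfied wearers is (1−u) × 0.70 + u × q.

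- u = 0.10, q = 0.50: 0.63 + 0.05 = 0.68
- u = 0.30, q = 0: 0.49 + 0 = 0.49

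Over u from 10% to 30% and q from 0% to 50%, a 70% result corresponds to 49% to 68% in the population that the hypothesis names.

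**The case against.** Enrolling asymptomatic wearers and asking how many remain so is a legitimate design. The Background section states the aim as the success rate of refitting, and the hypothesis claims neither attainment nor improvement. The entry limit is printed in the criteria, the study is labelled exploratory, and no test against 70% is planned. The Statistical Analysis section refers to scores below 12 as satisfied scores, which could fold the limit into the word. All of this stands as mitigation. It does not remove the point: Visit 1 and the Inclusion Criteria treat satisfaction and the score as two conditions, and a numerical threshold is still stated without its reference.

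Some stronger inferences are not supported:

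- *That 70% or more is to be presented as excellent comfort.* No section makes that link. The message also covers vision, satisfaction and recommendation, and VAS and Likert items measure comfort and satisfaction separately.
- *That the plan claims the result for all satisfied wearers.* It never says all; its wording is simply unrestricted.
- *That the study cannot show improvement.* Only the dichotomy cannot. The CLDEQ-8 score is a secondary endpoint and is collected at baseline and exit.
- *That a 70% result is a 30-point loss caused by the lens.* The no-effect reference is below 100%, and there is no control arm. If it were 80%, 21 or fewer of 30 would occur by chance with probability 0.13. A paired test of 9 losses to 0 gains (exact McNemar p = 0.0039) does not rescue this reading, because entry makes gains impossible.
- *That improvement of dry eye disease is promised.* The text says participants may experience it. It fits this sample poorly, but it is a separate wording error and adds no weight to the endpoint argument.

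**Conclusion.** The point holds as a matter of framing. It is not an arithmetic error, and the design need not change. The binary primary endpoint is 100% at baseline by construction and measures retention. The 70% threshold is not justified against that start: it is met by 21/30 with 9 newly symptomatic wearers, and would be met with probability about 0.94 or more with no lens effect. The population in the objective, hypothesis and message is wider than the one enrolled. The 100% baseline and the exact intervals follow from the Protocol alone. The 80% to 98% reference and the probabilities built on it rest on assumed means of 6 to 10, SDs of 4 to 6 and reliabilities of 0.7 to 0.9. The 49% to 68% range is only an illustration.

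**What to change.** 1. In the Study Objective, Study Hypothesis and clinical message, restrict the population to satisfied Infuse wearers with baseline CLDEQ-8 below 12.
2. In the Study Hypothesis, the Executive Summary design table and the Primary Endpoint, name the primary endpoint retention of CLDEQ-8 below 12.
3. Report the proportion who moved to 12 or more with its exact 95% interval, beside the paired change in CLDEQ-8 score. State that baseline is 100% by selection and that some loss is expected from retest variation.
4. Justify 70% against that reference, or present it as descriptive only.
5. Report how many satisfied wearers were screened out for a score of 12 or more.
6. Correct the statement under Potential Benefits of Participation about dry eye disease so that it fits the enrolled sample.

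Cost: wording and one screening count. Eligibility, visits and sample size are unchanged. The downside for the sponsor is a narrower claim.

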## Consent and Screening

All participants will undergo an informed consent process prior to the initiation of any study-related procedures.

Potential participants will not be provided with the informed consent form (ICF) prior to Visit 1. The informed consent process will take place on-site at the study visit. At that time, participants will be given sufficient time to review the ICF, ask questions, and discuss participation with study staff prior to signing. Written informed consent will be obtained before any study-specific procedures are performed.

Screening procedures will occur after informed consent is obtained and will include review of medical and ocular history, as well as any necessary clinical assessments to confirm eligibility. Eligibility will be determined based on the Inclusion and Exclusion Criteria outlined in the protocol. Only participants who meet all eligibility criteria will be enrolled in the study.

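### The acuity inclusion criterion gives 20/25 and 0.18 LogMAR as one threshold, but 20/25 is about 0.10 LogMAR and 0.18 LogMAR is about 20/30

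*Protocol*

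**What the plan says.** The Protocol, under Inclusion Criteria, sets one distance acuity threshold for each eye and writes it in two notations: "Best-corrected distance visual acuity (BCDVA) of at least 20/25 (0.18 LogMAR) or better in each eye". The threshold is not restated anywhere else, and no section says which notation takes precedence.

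The criterion is binding. Under Consent and Screening the Protocol states: "Only participants who meet all eligibility criteria will be enrolled in the study".

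LogMAR appears elsewhere as a measurement scale. At Visit 1 the procedures list "High-contrast LogMAR visual acuity measured at distance (20ft), intermediate (60cm), and near (40cm) with Infuse MF", followed by the same measurements with the study lens. Manifest refraction is a separate item in that list, and no notation or scoring rule is given for the best-corrected acuity that goes with it.

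**The concern.** A parenthesis after a Snellen fraction is read as its conversion. Here the conversion does not match, so the sentence contains two cut-offs, and the LogMAR one is the more lenient.

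What is at stake is consistent eligibility. A candidate with one eye between the two cut-offs can be accepted on one figure and refused on the other. Whichever figure the staff apply, someone checking against the other could record an eligibility deviation. Because the rule applies to each eye separately, one such eye is enough to put the candidate in dispute. Eligibility is fixed in the protocol, so a separate statistical analysis plan would not be expected to settle this.

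**Working it through.** **Inputs.** Both figures come from the Inclusion Criteria, which read "at least 20/25 (0.18 LogMAR) or better in each eye": a Snellen threshold of 20/25 and a LogMAR threshold of 0.18.

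**Formula.** LogMAR = log10(MAR), where MAR is the Snellen denominator divided by the numerator.

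**Step 1: try to reproduce the stated 0.18 from 20/25.**

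- log10(25/20) = log10(1.25) = 0.0969, which rounds to 0.10. The stated figure is not reproduced.
- Natural logarithm instead of base 10: ln(1.25) = 0.223. Not 0.18.
- Decimal acuity: 20/25 = 0.80. Not 0.18.

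**Step 2: find the acuity to which 0.18 belongs.**

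- Inverse: 20 × 10^0.18 = 30.3, so 0.18 LogMAR is about 20/30.
- Neighbouring lines:

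| Snellen | LogMAR |
|---|---|
| 20/25 | 0.097 |
| 20/30 | 0.176 |
| 20/32 | 0.204 |
| 20/40 | 0.301 |

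Only 20/30 rounds to 0.18.

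**Step 3: size of the gap.**

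- 0.18 − 0.0969 = 0.083 LogMAR. Rounding does not explain it, because 20/25 rounds to 0.10.
- If each letter counts 0.02 LogMAR (assumed), 0.083 / 0.02 = 4.2, or about 4 letters.

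**Step 4: which eyes fall between the two cut-offs.** This depends on scoring, which the Protocol does not fix for best-corrected acuity. The range is:

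- *Letter-by-letter scoring at 0.02 per letter (assumed).* Taking 20/25 as 0.10, eyes scoring 0.12, 0.14, 0.16 or 0.18 fail the Snellen figure and pass the LogMAR figure.
- *Snellen chart with a 20/30 line (assumed).* An eye reading 20/30 is at 0.176. It fails 20/25 and passes 0.18.
- *Whole-line scoring in 0.1 steps (assumed).* An eye at 0.1 passes both, taking 20/25 as 0.10, and an eye at 0.2 fails both. The two cut-offs then select the same eyes.

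**Step 5: number of candidates affected.** The Protocol gives no distribution of best-corrected acuity, so no estimate is possible. For scale only, each disputed participant would be 1/30 = 3.3% of the target sample, and the number could be zero.

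**The case against.** The strongest reply concedes the arithmetic and disputes its importance. The primary endpoint is the proportion with CLDEQ-8 below 12, and acuity does not enter its calculation. The study has one arm and describes itself as exploratory, so there is no between-arm comparison for differing eligibility to bias. The disputed band is less than one 0.1 line wide, and under whole-line scoring it may contain no eyes. All of this stands, and it limits the severity.

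Three stronger readings are tempting, and the documents do not support them:

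- *That staff would apply 0.18 because the study measures acuity in LogMAR.* The LogMAR measurements at Visit 1 are taken with the multifocal lenses on the eye. The criterion concerns best-corrected acuity, for which no notation is given, and it puts the Snellen figure first. Staff could equally apply 20/25.
- *That the discrepancy adds spread to the visual acuity endpoint.* That secondary endpoint is binocular, measured through multifocal lenses at three distances. The criterion is per eye and best-corrected at distance. Nothing in the Protocol allows a difference of 0.083 in the latter to be carried over to the former.
- *That the study population is ill-defined.* The ambiguity is confined to a narrow band of one criterion and is not shown to affect anyone.

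The reply does not remove the contradiction. The text is a current enrolment criterion, every criterion must be met, and nothing else in the Protocol resolves it.

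**Conclusion.** The criterion is wrong as written: it equates two acuities that differ by 0.083 LogMAR. The conversion itself needs no assumption beyond the definition of LogMAR. The equivalence to about 4 letters assumes 0.02 LogMAR per letter, and the practical effect ranges from none (whole-line scoring in 0.1 steps) to that amount. The calculation of the primary endpoint is not touched. The document does not show which figure was intended, so no view is taken on that. Severity is low to moderate: this is an error in an operative enrolment threshold, with a consequence that is limited and cannot be quantified from the document.

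**What to change.** Before enrolment, the sponsor should decide which threshold was meant and state it with its correct equivalent: either 20/25 with 0.10 LogMAR, or 20/30 with 0.18 LogMAR. The same number should go into the eligibility CRF.

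The cost is one corrected figure in the Inclusion Criteria and a matching entry in the CRF. The design, sample size and analysis do not change. If the correction is left until after enrolment has begun, the eligibility of participants already enrolled would have to be checked again.

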### Exclusion Criteria:

- Presence of active ocular infection, inflammation, or clinically significant ocular surface disease (e.g., severe dry eye, pterygium, or keratoconus).
- Uncontrolled systemic disease or use of systemic medications known to significantly affect the tear film (e.g., antihistamines or isotretinoin), unless on a stable dose for  $\geq 90$  days.
- History of refractive surgery (LASIK, PRK, RK) or intraocular surgery (Cataract/IOL)
- Clinically significant ectropion, entropion, or trichiasis that may interfere with lens performance (4).
- Baseline Corneal Fluorescein Staining (CFS) score of  $>2$  in any single zone of the NEI/Industry scale (6).
- Subjects currently wearing a monovision or modified-monovision contact lens fit.
- Subjects who are pregnant or lactating (due to hormonal fluctuations affecting the tear film).
- Participation in any other clinical trial within the past 30 days of enrollment.

## Statistical Analysis

The Primary Endpoint will be summarized as the proportion of participants who have satisfied CLDEQ-8 scores (scores <12). Questionnaire scores will be presented with descriptive statistics.

Primary endpoint reported with exact (Clopper–Pearson) 95% confidence intervals.

Data will be captured and managed using REDCap electronic data tools. Data Analysis Plan Statistical analysis will be performed using SPSS v28.0 or Stata.

The study will enroll 30 subjects (60 eyes) who are habitual, satisfied wearers of Bausch + Lomb Infuse Multifocal lenses.

## Sample Size Justification

Target enrollment: 30 participants. This will be a prospective study to understand if satisfied Infuse Multifocal CL wearers can be successfully refit into Dailies Total1 Multifocal CLs. The Primary Endpoint will be simply analyzed as the proportion of subjects who have CLDEQ-8 scores  $<12$  at the end of the study. We estimate that 30 completed subjects will be enough to gain a general understanding of CL success and patient reported outcomes based upon past research (Duong et al., 2021a; Duong et al., 2021b). A sample size of  $N=30$  would satisfy the requirements of the Central Limit Theorem, ensuring the normality of the sampling distribution for parametric testing. Thus, 33 subjects can be recruited, so if a subject drops out before completing the study, they will be replaced.

The study is exploratory and not powered as a confirmatory superiority trial.

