## Study Background & Unmet Medical Need

### Background:

Despite advancements in contact lens (CL) technology, presbyopic patients often experience discomfort and dissatisfaction, leading to high dropout rates. This study aims to determine the success rate of refitting current, satisfied wearers of Bausch + Lomb Infuse Multifocal (kalifilcon A) contact lenses into DAILIES TOTAL1 Multifocal (delefilcon A) contact lenses. The goal is to understand how satisfied multifocal CL wearers respond to being refitted into an alternative daily disposable CL brand with different material properties and designs. This information will be valuable for clinicians when considering transitions due to patient preference, cost, material discontinuation, or the availability of newer technologies.

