## Early Withdrawal of Subjects

Participants may be withdrawn from the study prior to completion for the following reasons:

- Voluntary withdrawal of consent at any time
- Occurrence of adverse events or safety concerns
- Failure to comply with study procedures or protocol requirements
- Investigator determination that continued participation is not in the participant's best interest

In the event of early withdrawal or study termination, participants may be asked to return any unused study materials, including contact lenses, if applicable. The reason for withdrawal will be documented when available.

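### Replacing dropouts to reach 30 completers in effect leaves lens-related dropouts out of the primary proportion, which can overstate the refit success rate by up to 6 to 9 points

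*Protocol*

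**What the plan says.** The Background section of the protocol gives the aim: "This study aims to determine the success rate of refitting current, satisfied wearers". The primary endpoint is the proportion of participants with a CLDEQ-8 score below 12 "after 2-weeks of wearing DAILIES TOTAL1 Multifocal (w finalized prescription"). The Study Hypothesis in the Executive Summary expects at least 70%.

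The Sample Size Justification sets the target in terms of completers: "We estimate that 30 completed subjects will be enough to gain a general understanding of CL success". It then gives the replacement rule: "Thus, 33 subjects can be recruited, so if a subject drops out before completing the study, they will be replaced". The Executive Summary carries the same pair of numbers, 30 and 33, and attributes the difference to dropout. The Statistical Analysis section has only the smaller one: "The study will enroll 30 subjects (60 eyes) who are habitual, satisfied wearers of Bausch + Lomb Infuse Multifocal lenses".

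The Study Assessments table schedules the CLDEQ-8 at Visits 1 and 3 only. Early Withdrawal of Subjects lists voluntary withdrawal, adverse events or safety concerns, non-compliance and investigator judgement as reasons for leaving. It names no questionnaire at early exit. Nothing in the protocol counts a dropout as a non-success.

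**The concern.** In a refit study, a participant who gives up the new lens because it is uncomfortable or blurred is a failed refit. Everyone enters satisfied with the habitual lens and with a CLDEQ-8 below 12, so deterioration on the new lens is what the endpoint has to detect. A participant who leaves before Visit 3 for that reason has no follow-up score, and the replacement rule puts someone else in that place. The reported figure then describes people who stayed in the lens, while the stated aim concerns everyone who was refitted.

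The study has one arm, so there is no comparator in which such a bias could cancel. The exact confidence interval reflects sampling error only and does not allow for it. The result is meant to support a clinical message about the lens, so the choice of denominator affects what can be claimed.

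**Working it through.** **Inputs from the protocol.** Target of 30 completers; ceiling of 33 recruited; dropouts replaced; hypothesised proportion at least 70%; exact (Clopper–Pearson) two-sided 95% interval. No dropout rate is stated.

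**The plan's own figure.** Inflating 30 by N/(1 − d) gives:
- d = 5%: 30/0.95 = 31.6, rounded up to 32
- d = 8%: 30/0.92 = 32.6, rounded up to 33
- d = 3/33 = 9.1%: 30/(30/33) = 33
- d = 10%: 30/0.90 = 33.3, rounded up to 34 (the simpler 30 × 1.10 gives 33)

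So 33 agrees with 30 completers plus an allowance of about 9 to 10% for dropout. That supports reading 30 as the number expected to have a Visit 3 score.

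**Bias formula.** Let p be the success proportion among 30 completers, k the number of replaced dropouts, and s the proportion of those dropouts who would count as successes. The all-dispensed proportion is (30p + ks)/(30 + k). The completer figure exceeds it by

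k(p − s)/(30 + k).

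This is zero if k = 0 or s = p. It is largest when s = 0, that is, when every dropout is a lens failure. With k = 3 and s = 0 it is p × 3/33 = p/11.

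**Worst case within the ceiling (k = 3, s = 0), with exact 95% intervals:**

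| Completers | All dispensed | Excess |
|---|---|---|
| 21/30 = 70.0% (50.6–85.3) | 21/33 = 63.6% (45.1–79.6) | 6.4 points |
| 24/30 = 80.0% (61.4–92.3) | 24/33 = 72.7% (54.5–86.7) | 7.3 points |
| 27/30 = 90.0% (73.5–97.9) | 27/33 = 81.8% (64.5–93.0) | 8.2 points |
| 30/30 = 100% (88.4–100) | 30/33 = 90.9% (75.7–98.1) | 9.1 points |

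**Fewer dropouts, all failures.** 21/30 = 70.0% becomes 21/31 = 67.7% with one and 21/32 = 65.6% with two.

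**Effect on the 70% hypothesis, read as the observed proportion.** On 30 completers, 21 successes are enough (0.70 × 30 = 21). On 33 dispensed, 24 are needed (0.70 × 33 = 23.1). Three results change sides:
- 21: 70.0% becomes 63.6%
- 22: 73.3% becomes 66.7%
- 23: 76.7% becomes 69.7%

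**Scale.** At 21/30 the half-width of the interval is (85.3 − 50.6)/2, about 17 points. The worst-case bias of 6.4 points is smaller than that, but it runs in one direction and the interval does not include it.

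**The case against.** The strongest reply is that replacement governs how many people are recruited, not who is analysed. The protocol never names a completer analysis set. It speaks of participants and subjects, and all 33 could be analysed under the present wording. Analysis sets are often left to the SAP, which is not at hand. It is right that the completer denominator is inferred. But a completer target, replacement of dropouts and an outcome that exists only at Visit 3 all point the same way, and the first two are rules the protocol itself states. An SAP could add an all-dispensed analysis, but it would not remove them.

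It can also be said that the study is exploratory and descriptive, that at most three spare places are involved, and that Visit 2 allows power changes that may prevent some failures. These points limit the importance of the bias. They do not remove it.

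A third reply is that counting every non-completer as a non-success turns a symptom endpoint into a composite of symptoms and retention. That is fair. It is one defensible choice among several, and best-case and worst-case bounds are another.

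Three stronger readings are tempting, but the protocol does not support them:
- **That people who wear the lens too little are swapped out.** The wearing schedule appears as willingness to adhere, in the inclusion criteria. "Failure to comply with study procedures or protocol requirements" is a reason for which a participant may, not must, be withdrawn, and only someone who drops out is replaced. An under-wearer can reach Visit 3 and be counted.
- **That the bias must always favour the study lens.** Voluntary withdrawal and investigator judgement need not relate to the lens. If dropouts would have done as well as completers, the completer figure is unbiased and the all-dispensed rule would err downward.
- **That 27/30 loses its result because the lower confidence limit falls from 73.5% to 64.5%.** The protocol has no rule comparing the lower limit with 70%. On the observed proportion, 27/33 = 81.8% still meets the hypothesis.

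**Conclusion.** The point holds in a limited form. Followed as written, the plan will in effect report success among completers, while its stated question is the success rate of refitting. The reported rate is too high to the extent that participants leave because of the lens.

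The size runs from zero (no dropouts, or dropouts who would have succeeded at the completers' rate) to 6.4 points at 70% and 9.1 points at 100%. The upper figures assume that all three spare places are used, that all three dropouts are lens failures, and that recruitment stops at 33. Within that worst case, only 21, 22 or 23 successes of 30 would change whether the observed proportion reaches 70%.

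This does not undermine an exploratory study. It is a predictable weakness that is cheap to correct before enrolment and hard to correct convincingly once results are known.

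**What to change.** Amend the Statistical Analysis and Sample Size Justification sections as follows:

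1. Make the primary denominator every participant dispensed DAILIES TOTAL1 Multifocal at Visit 1. Participants added after a dropout join the denominator and do not substitute for the person who left.
2. Count discontinuation without a Visit 3 CLDEQ-8 as non-success.
3. Report all dropouts with their reasons.
4. Give as supportive results the completer proportion and a version that excludes withdrawals clearly unrelated to the lens.
5. Reconcile the 30 to be enrolled in Statistical Analysis with the 33 who can be recruited in Sample Size Justification.

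The change needs no extra participants or visits. Its cost is a slightly less favourable headline figure if anyone drops out, and a few lens-unrelated dropouts counted as failures. The supportive analyses show how much that matters.
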